2.1 Background information

The human head louse *Pediculus humanus capitis* is an obligate parasitic insect, adapted to life in human hair, that spreads largely through head-to-head contact between infested and uninfested individuals. It is therefore to be expected that infestations spread most readily between people who are in frequent physical contact with each other; typically, younger children in the same school class and close family groups¹.

Effective methods for the eradication of an infestation, such as wet-combing and the use of proprietary head lice treatment preparations, are readily available. Most methods are time-consuming, require diligence and some preparations may be expensive. Ineffective application of insecticidal treatments in the past have led to the spread of resistant strains, the so-called "Super Lice". In many cases, the product has to be left in the hair for a set period, then washed out. A product that can be easily applied, then left in the hair for an unspecified period adds the element of convenience when time constraints do not allow the aforementioned approach to be taken.

Vamousse Spray 'n' Go is a member of broad-spectrum antiparasitic products which may have a unique mode of action. Compounds of the class containing IPA 99%, Geraniol and Linalool has potential cause of death primarily through by suffocating lice and/or dissolves the bugs' exoskeletons and dehydrates them.

2.2 Rationale

An effective treatment is much needed to lower patient re-infestations, thus lowering out of pocket cost on lice treatment, multiple pediculicides and/or remedies, as well as nit combs for delousing and nit removal, including loss time spent on doctor's office visits and finally manual delousing and removal of the nits.

The proposed study is aimed to evaluate the safety and efficacy of Vamousse Spray 'n' Go. An Open Label study has been selected

in order to evaluate the efficacy and safety of Alliance Pharmaceuticals Ltd. Vamousse Spray 'n' Go in the treatment of head lice.

Each subject will be selected according to predefined inclusion and exclusion criteria. The study treatment duration of 15 days is expected to be sufficient.

2.3 Potential Risks and Benefits

2.3.1 Known potential risks

SAFETY DATA SHEET Vamousse Spray 'n' Go Date Prepared: 3/03/2021

Information on Toxicological Effects:

Potential Health Effects:

- Eye Contact: May cause mild eye transient irritation with redness and tearing.
- Skin contact: Skin Sensitization, May cause an allergic skin reaction. May cause mild irritation. Prolonged or repeated contact may cause defatting of the skin with dryness and cracking.
- Inhalation: May cause allergy or asthma symptoms or breathing difficulties if inhaled. Breathing vapors or mists may cause irritation of the mucous membranes and upper respiratory tract. Excessive overexposure may cause headache, dizziness, and drowsiness.
- Ingestion: Ingestion is an unlikely route of exposure, this material can be harmful if swallowed. It may cause depression of the central nervous system, nausea, and vomiting. May be fatal if swallowed and enters airways.

Other Information: A theoretical concern exists about medication errors that might result in the ingestion of the Vamousse Spray 'n' Go product (particularly in young children), therefore it should only be administered under the direct supervision of an adult.

2.3.2 Potential benefits

A demonstration of efficacy and safety with a single treatment application; spraying treatment completely saturate each section in showing safe to leave on overnight allowing hair to dry naturally with 8 hours exposure time. Vamousse Spray 'n' Go represents a significant addition to the current armamentarium for the treatment of head lice.

3. Objectives and Purpose

The study will explore whether treatment with Vamousse Spray 'n' Go is:

- more effective in killing lice & eggs compared to a permethrin-based control product.
- Clinically proven to kill lice & eggs, including super lice,
- Convenient to use - Spray 'n' Go can be left in the hair for the duration of the school day or overnight,
- works with one application or with re-application after 7 days if necessary,
- cosmetically acceptable/smells good/fast-drying,
- safe to use in children 2yo+

4. Study Design and Endpoints

4.1 Description of the Study Design

This is a Study to Evaluate the Safety and Efficacy of Alliance Pharmaceutical Product in Subjects Infested with Pediculosis Capitis. The subject population includes healthy male and female subjects aged 2 years and up who are infested with *Pediculus humanus capitinis*. Household members infestation with an active head lice, defined as at least 1 live louse (adult and/or nymph) present on the scalp and/or hair as determined by a trained evaluator, will receive treatment with study product at baseline.

The planned overall sample size for this clinical trial is approximately n=58 subjects, equally divided between treatment and control groups. Potential subjects will be screened for eligibility and if eligible to participate, their infestation level will be rated. Eligible subjects at each infestation level will be assigned alternately to the treatment or control group to ensure that the two groups have approximately equal representations of infestation severity levels. Level of infestation will be rated as heavy, moderate or light described by how quickly lice were found during combing: heavy infestation = >1 louse with one stroke of the comb; moderate infestation = 1 louse with one stroke of the comb; light infestation = first louse found only after several strokes of the comb

After assignment to a study group, each eligible subject will receive the application of either the Alliance Pharmaceutical Product Vamousse Spray 'n' Go drug or the Permethrin-based control drug. Infested household members will be treated with the Vamousse Spray 'n' Go or Permethrin lotion on-site (i.e., the household members should be assigned to the same treatment as the index case). During the baseline visit (Day 0), the Investigator and clinical staff members will record subject's demographics; elicit informed consent; obtain medical history; review concomitant medication to identify any prohibited therapies the subject may be receiving; collect vital signs; conduct visual assessment of head lice, specifically counting live lice and nits with stages noted, using a 15 inch led 5x magnifying procedure lamp and if needed for confirmation, laboratory microscopes; perform physical examination; assess local skin/ scalp irritation; assess ocular irritation; perform urine pregnancy test on females; and conduct an adverse event assessment.

At day 7, if live lice are still present, a repeat treatment will be administered. After day 7 if a subject reports clear signs of infestation (i.e., the presence of live lice), they will be regarded as a treatment failure and they will be offered treatment with an alternative product (viz., Vamousse Mousse) by clinical staff.

For the treatment group, Clinical staff will apply Vamousse Spray 'n' Go to fully coat dry hair and scalp, avoiding the eyes and mucus membranes. The Treatment will be left on the hair and scalp for 8 hours, then standard at home shampoo and rinsed off with warm water, followed by combing. The Treatment spray bottle is intended for a single use although it contains a sufficient quantity for two treatments. All household members will be instructed on an overall lice management program, which includes:

- Wash (in hot water) or dry-clean all recently worn clothing, hats, used bedding and towels.
- Wash (in hot water) personal care items such as combs, brushes and hair clips.
- Record time and date product shampoo/rinse 8 hours post treatment

For the control group, Clinical staff will first shampoo the hair and scalp using regular shampoo. They will then

thoroughly rinse and towel dry the hair and scalp, and allow hair to air dry for a few minutes. Shaking the permethrin lotion well before applying, they will proceed to thoroughly wet the hair and scalp with the permethrin lotion, being sure also to cover the areas behind the ears and on the back of the neck. After allowing the lotion to remain in place for 10 minutes, they will then rinse the hair and scalp thoroughly and dry with a clean towel.

The site will provide Subject with lice management instructions. Subjects will return for post-baseline visits assessments at Day 2, Day 7, and Day 14.

Day 2: The Investigator and medical staff will collect medical history, collect vital signs, perform physical examination, scalp irritation assessment, ocular irritation assessment and adverse events assessment, perform a visual assessment for the presence or absence of head lice, (Lice will be counted, each stage examined and noted live or dead; 15in led 5x magnifying procedure lamp or laboratory microscopes are used for confirmation if needed, Without clipping hair strands, nits will also be examined, each stage examined and noted hatched or unhatched), and adverse events assessment Urine pregnancy testing will be performed on each Visit, with interim visits confirming pregnancy has not occurred through questioning participating subject and legal guardian.

Day 7: The Investigator and medical staff will collect medical history, collect vital signs, perform a physical examination, assess scalp irritation, assess ocular irritation and adverse events, perform a visual assessment for the presence of head lice (lice will be counted, each stage identified, and noted live or dead; 15in led 5x magnifying procedure lamp or laboratory microscopes will be used for confirmation if needed; without clipping hair strands, nits will also be examined, each stage examined, and noted hatched or unhatched). Urine pregnancy testing of females will be performed on each visit, with interim visits confirming pregnancy has not occurred through questioning participating subject and legal guardian. If, at day 7, live lice are still present, a repeat Vamousse Spray 'n' Go or Permethrin (depending on study group) shampoo treatment will be administered.

Day 14: The Investigator and medical staff will collect medical history, concomitant and prohibited medication review, perform vital signs, urine pregnancy testing if applicable, perform physical examination, record local application site reactions, ocular irritation assessment, perform a visual assessment for the presence of head lice (lice will be removed, counted, each stage examined and noted live or dead; 15 inch led 5x magnifying procedure lamp or laboratory microscopes are used for confirmation; nits will also be removed by clipping hair strands, examined, each stage counted, and noted as hatched or unhatched) and adverse events assessment. By day 14 if a subject reports clear signs of infestation (i.e., the presence of live lice) they will be regarded as a treatment failure and will be offered treatment with an alternative product (Vamousse Mousse) by clinical staff.

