SOC	System Organ Class
SOP	Standard Operating Procedure
SUSAR	Suspected Unexpected Serious Adverse Event
TEAE	Treatment Emergent Adverse Event
US	United States
WHO	World Health Organization

Protocol Number: ALLIO10 - 0021
Version 3.0; 27 July 2022

INVESTIGATOR SIGNATURE PAGE

The signature below constitutes approval of this protocol and provides the necessary assurance that this study will be conducted at his/her investigational site according to all stipulations of the protocol including all statements of confidentiality and in accordance with International Conference on Harmonisation (ICH) Good Clinical Practice (GCP) and local regulatory requirements.

Print Name	[name], APRN, PI
Title	Principal Investigator
Address of Institution/ Site	South Florida Family Health and Research Centers, LLC. DBA: Lice Cleanique [name], USA
[contact]

INVESTIGATOR SIGNATURE

07/28/2022
DATE

1. Synopsis

Study Title	Treatment of infestation with Pediculus humanus capitis in the community using a leave-in spray: A prospective, randomised controlled study.
Protocol Number	ALLI010-0021
Development Phase	Post-marketing confirmatory
Type of Study	Safety and efficacy
Test Product	Vamousse Spray 'n' Go
Name of Active Ingredient	Natrum Muriaticum 2X (HPUS)
Route, Dose, & Regimen	
Route: Topical application
 
Dose: Spray treatment to completely saturate each section. Work through hair with a comb to ensure full coverage down to the scalp. Thoroughly saturate all hair and scalp.
 
Regimen: Allow hair to dry naturally. Leave treatment in for a minimum of 8 hours

Control Product	Nix Creme Rinse Lice Treatment
Name of Active Ingredient	1% Permethrin
Route, Dose, & Regimen	
Route: Topical application
 
Dose: Thoroughly wet the hair and scalp with the permethrin lotion. Be sure to cover the areas behind the ears and on the back of the neck also. Allow the lotion to remain in place for 10 minutes.
 
Regimen: Rinse the hair and scalp thoroughly and dry with a clean towel.

Sponsor	Alliance Pharmaceuticals Ltd. [name], United Kingdom

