7.3 Study schedule

7.3.1 Screening/randomization

Screening Visit Day 0 (Visit 1)

- Obtain informed consent of potential participant verified by signature on written informed consent.
- Record demographic information, obtain medical history, and history of head lice.
- Review medications history and concomitant/prohibited medications to determine eligibility
- Verify inclusion/exclusion criteria.
- Collect urine sample for pregnancy testing for all subjects of childbearing potential.
- Perform assessment for living head lice on subjects and household members for a minimum of 15 minutes. Each subject must have at least 1 live louse. Rate severity of infestation. After each subject has been identified, additional infested household members will also be assessed for infestation.
- Level of infestation will be rated as heavy, moderate or light described by how quickly lice were found during combing: heavy infestation = >1 louse with one stroke of the comb; moderate infestation = 1 louse with one stroke of the comb; light infestation = first louse found only after several strokes of the comb
- Household members must have an active head lice infestation defined as: At least 1 live lice (adult and/or nymph) present on the scalp and/or hair, as determined by a trained evaluator. Household members will be assigned to the same study group as index case.
- Schedule study visits for participants who are eligible and available for the duration of the study.
- Randomly assign subjects to treatment or control group based on infestation severity alternation system (i.e., randomly assign pairs of equal severity levels to treatment and control groups, a form of stratified random sampling) to achieve balanced representation of severity in the two groups.
- Investigational Product Dispensation/ Application for subject.
- Provide each subject with homecare instructions including combing after first wash out.
- Inform subject when to come back for each follow-up visit.
- Provide Standard of Care treatment on-site to unqualified infested household members.

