10.2 Data sets to be evaluated

The subject populations are defined as follows:

Safety Population includes all subjects who were administered treatment. This is the population that will be used for the safety assessments.

Modified Intent-to-Treat (mITT) population includes all subjects who met all inclusion/exclusion criteria, were randomized, administered treatment, and had at least one post-treatment efficacy evaluation. This is the primary population for determination of the effectiveness of the active treatment.

Per-Protocol (PP) population includes all mITT subjects who were administered treatment, had no protocol deviations which could have interfered with the accurate assessment of treatment efficacy, and returned for the Day 14 visit within the allowed window. This is the primary population for the efficacy comparisons between the two active treatment groups.

Subjects whose condition worsens and require alternate or supplemental therapy for the treatment of head lice during the study will be discontinued, included in both the mITT and PP population analyses as treatment failures. Subjects who discontinue early for reasons other than treatment failure will be excluded from the PP population, but included in the mITT population, using Last Observation Carried Forward (LOCF).

Efficacy analyses will be performed on both the per-protocol population and the mITT population. Safety analyses will be performed using the Safety population as defined.

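### Section 4.1 assigns subjects by alternation and section 7.3.1 by random pairs; neither describes concealment, so much of the allocation is foreseeable in an open-label trial called randomised

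*Combined protocol and SAP*

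**What the plan says.** The study title calls the trial "A prospective, randomised controlled study". The mITT definition in section 10.2 admits only subjects who "were randomized, administered treatment, and had at least one post-treatment efficacy evaluation".

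Two sections describe how arms are assigned:

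- Section 4.1: "Eligible subjects at each infestation level will be assigned alternately to the treatment or control group". The stated aim is similar severity in the two groups. No random element appears.
- Section 7.3.1: "Randomly assign subjects to treatment or control group based on infestation severity alternation system", explained in brackets as "randomly assign pairs of equal severity levels to treatment and control groups".

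Both sections use three severity levels (heavy, moderate, light), judged by how quickly combing finds lice. In section 7.3.1 the rating comes before assignment: "Each subject must have at least 1 live louse. Rate severity of infestation". Other infested members of the household follow the first: "Household members will be assigned to the same study group as index case".

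Section 2.2 states "An Open Label study has been selected". The synopsis names one centre and about 58 subjects, and section 6.1.7 puts screening and treatment on the same day. The available text, including the section headed Screening/randomization, does not say how the sequence is produced, who keeps it, or when an allocation is disclosed.

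**The concern.** Alternation is not randomisation, so staff who follow section 4.1 carry out a different procedure from staff who follow section 7.3.1. Under 4.1, the randomisation step that the mITT definition requires does not take place.

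The setting makes foreknowledge realistic. Clinical staff apply two visibly different products at a single site, so they know every earlier allocation. The same site rates severity, and severity selects the queue from which the next arm comes. When the next arm is known or easily guessed, three things can depend on it: whether a subject is enrolled, when they enter, and how their severity is rated. Eligibility leaves room for judgement, for example on general health and likely compliance.

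Balancing three coarse severity levels does not protect against selection on other factors. The unadjusted Z test in section 10.1 cannot remove a resulting difference in prognosis, and adjustment for measured covariates could not remove the unmeasured part.

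**Working it through.** **Inputs.** From the synopsis and section 10.5: 58 enrolled, 52 completers, 45% versus 85% lice free, two-sided alpha 0.05, power 80%, 1:1 allocation. From section 4.1: three severity levels. The number of index cases K is not given; 19, 29 and 58 are assumed to show the range.

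**The plan's own figure.** For 45% versus 85%, the two-proportion formula gives 21.1 per arm without continuity correction and 25.9 with it. The corrected value rounds up to the protocol's 26 per group (52). With 10% dropout, 26/0.9 = 28.9, so 29 per group (58). The sample size reproduces, and 58 is the denominator below.

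**Alternation (section 4.1, literal).** With an unknown starting arm in each level and individual assignment, only the first subject in each level is unpredictable once severity is known:

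- (58 − 3)/58 = 55/58 = 94.8%.
- If the starting arm is fixed or known, 100%.
- Counted per index case, (K − 3)/K: 16/19 = 84%, 26/29 = 90%, 55/58 = 95%.

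Before severity is rated, the arm is certain only when all three queues point the same way.

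**Random pairs (section 7.3.1), filled in order of arrival.** The second index case of each pair is certain. With o levels of odd size (0 to 3), certain = (K − o)/2 and best guess = [certain + 0.5 × (K − certain)]/K.

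| Index cases K | Certain | Share certain | Best guess correct |
|---|---|---|---|
| 58 | 28–29 | 48–50% | 74–75% |
| 29 | 13–14 | 45–48% | 72–74% |
| 19 | 8–9 | 42–47% | 71–74% |

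Example, K = 58 with two odd levels: (58 − 2)/2 = 28; (28 + 0.5 × 30)/58 = 43/58 = 74%.

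These are shares of index-case allocations. Household members' arms are also known once the index case is assigned. Counted over all 58 subjects with 29 households, the certain share is (29 + 13)/58 to (29 + 14)/58, or 72–74%.

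**Varying blocks of 4 and 6.** Simulation used equally likely sizes, three strata, 1,000 runs for each of three severity mixes, and an observer who knows the sizes but not the current block.

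- Certain: 5–6% of index allocations.
- Best guess: 68%, 67% and 66% for K = 58, 29 and 19.
- 95th percentile of the arm difference at K = 58: 4 subjects.

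If block boundaries were known and blocks complete, the certain share would be (1.333 + 1.5)/10 = 28% and the best guess (2.833 + 4.1)/10 = 69%.

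**Cost in power** (52 completers, continuity-corrected, clustering ignored, control:treatment): 26:26, 0.803; 28:24, 0.797; 24:28, 0.803; 32:20, 0.766; 20:32, 0.788.

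**The case against.** The strongest reply is that only one scheme was intended. Section 7.3.1 uses the word alternation itself and explains it as random pairs. Section 4.1 is a design summary with the same aim, so its wording may be loose shorthand. That is possible, and on that reading the 95% falls away. It does not clear the plan: the sections still differ as written, and unconcealed pairs still leave about half of index allocations certain.

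A second reply is that pairs drawn jointly, with both members present, would give no certain allocations. That is true, but no such step is described, and same-day screening and treatment leaves little room for it. Section 7.3.6 allows rescreening within a week for subjects who cannot return within 24 hours. This weakens the timing argument somewhat, but does not establish joint draws.

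A third is that the two headline figures compare like with like only if all 58 subjects are index cases. This stands, and the range over K is shown for that reason.

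Finally, the opening for manipulation is mainly at or after the severity rating, no bias has been quantified, and varying blocks improve guessing only modestly. All of this is fair. It limits the claim to exposure and leaves the defect in place.

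**Conclusion.** The concern holds. Section 4.1 as written gives a non-random, foreseeable allocation, it conflicts with section 7.3.1, and neither section describes sequence generation or concealment. This must be corrected before the trial can be described as randomised.

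The size depends on the reading. Under alternation, at least 95% of 58 individual assignments are determined once severity is known, given staff who know earlier allocations and an unknown start in each of three levels. Under sequentially filled pairs, 42–50% of index allocations are certain and 71–75% are guessed correctly, for an assumed 19 to 58 index cases. If pairs were drawn jointly, the pair figures would not apply.

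The conflict and the silence on concealment are certain from the text. Whether bias would follow, and how much, cannot be derived from the documents.

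**What to change.** Replace the allocation wording in sections 4.1 and 7.3.1 with one procedure:

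- a computer-generated random list, prepared and held by someone outside the recruiting staff;
- stratification by the index case's severity, with the household allocated as a unit;
- varying block sizes not disclosed to the site, for example 4 and 6;
- release of each allocation only after consent, eligibility, severity rating and the participating household members are recorded.

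The essential elements are a single random rule and concealed release; the block sizes are one workable choice. Against sequential pairs, certain foreknowledge falls from 42–50% to about 6%, even for someone who knows the sizes. It would be 28% if block boundaries became known. Best-guess accuracy falls only 5–8 points, to about 66–68%.

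The cost is one list, an off-site release route and revised wording, with N unchanged. Recording household members first may lengthen the Day 0 visit. Arms may be less equal. If every subject is an index case, a difference of 4 (28:24 among 52) leaves power at about 80%. An illustrative 32:20 split in either direction gives 77–79%, 1–3 points below target. Household allocation could widen the difference by an amount that depends on household sizes the protocol does not give.

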4.2.2 Primary Endpoint

The proportions of participants in each of the study groups (i.e., treatment and control) who are completely free of live adult lice and nymphs at day 14

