5.5 Subject withdrawal and termination

5.5.1 Potential reasons for withdrawal

In accordance with the Declaration of Helsinki and other applicable regulations, a subject has the right to withdraw from the study at any time and for any reason without prejudice to his or her future medical care. The Investigator or Medical Monitor may also withdraw the subject at any time if it is medically necessary or in the interest of subject safety.

A subject will be discontinued from this study if any of the following criteria are met:

1. Withdrawal of consent by the subject is received. In the opinion of the Investigator or Medical Monitor it is not in the subject's best interests to continue in the study.
2. Occurrence of an Adverse Event (AE) or Serious Adverse Event (SAE), which, in the opinion of the Investigator, warrants discontinuation of the subject from the study.
3. Pregnancy as informed by the subject or as determined by a positive urine pregnancy test.
4. Significant non-compliance with study procedures that would interfere with the study results or increase the subject's risks in the study, as determined by the Investigator.
5. Subject is deemed to be a treatment failure if upon revisit it is determined that they are still infested having live lice. They will be terminated from the study and provided the standard of care at that point in the study.
6. Any clinical adverse event (AE), laboratory abnormality, or other medical condition or situation occurs such that continued participation in the study would not be in the best interest of the participant.
7. The participant meets an exclusion criterion (either newly developed or not previously recognized) that precludes further study participation.

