7.3.4 Final study visits

Visit Day 14 (Visit 4) (+/- 2 days)

- Medical History, Physical Examination, Vital Signs, Urine Pregnancy Test, Head Lice Visual Assessment, Local Skin/Scalp Irritation Assessment, Ocular Irritation Assessment,
- Concomitant and Prohibited Medication Review and record results on Source Document.
- Record adverse events as reported by participant or observed by investigator.
- Perform assessment for living head lice on subject for visual confirmation of infestation for a minimum of 15 minutes.
- If, after day 14, a subject reports clear signs of infestation i.e., the presence of live lice, they will be regarded as a treatment failure and they will be offered treatment with an alternative product, Vamousse Mousse.

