7.6 Rescue medication, treatment and procedures

If live lice are present on Day 14, the subject will receive the over-the-counter (OTC) rescue treatment, Vamousse Mousse, for head lice and their study participation will be considered complete and will be considered a treatment failure.

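### A subject's unconfirmed report of live lice can fix treatment failure before the Day 14 examination in an open-label trial, while other sections rest failure on lice being found

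*Combined protocol and SAP*

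**What the plan says.** Three passages let the subject's own report decide failure:

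- Section 4.1, general description: "After day 7 if a subject reports clear signs of infestation (i.e., the presence of live lice), they will be regarded as a treatment failure".
- Section 4.1, Day 14 paragraph: "By day 14 if a subject reports clear signs of infestation (i.e., the presence of live lice) they will be regarded as a treatment failure".
- Section 7.3.4: "If, after day 14, a subject reports clear signs of infestation i.e., the presence of live lice, they will be regarded as a treatment failure".

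Two passages rest it on lice being found:

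- Section 5.5.1, item 5: "Subject is deemed to be a treatment failure if upon revisit it is determined that they are still infested having live lice".
- Section 7.6: "If live lice are present on Day 14, the subject will receive the over-the-counter (OTC) rescue treatment".

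The primary endpoint in 4.2.2 is the proportion "completely free of live adult lice and nymphs at day 14". Section 7.3.4 has staff inspect for at least 15 minutes at that visit. Section 10.2 deals with subjects whose condition worsens and who need alternate or supplemental head lice therapy: they "will be discontinued, included in both the mITT and PP population analyses as treatment failures". Section 7.3.5 leaves an unscheduled examination to the investigator's discretion. The Synopsis and section 2.2 call the trial open label.

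**The concern.** Entry requires a live louse identified by a trained evaluator, and lice at follow-up are classed as live or dead under magnification. A report from home carries no such check. A caregiver could take dead lice, nits or debris for live lice, and readiness to report could depend on the product used. An 8-hour leave-in spray and a 10-minute rinse cannot be confused, so every household knows its arm.

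If a mistaken report leads to the alternative product, the later examination can no longer show what the assigned treatment achieved. Any difference between arms in mistaken reports then passes directly into the primary comparison.

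**Working it through.** **1. The rules side by side**

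| Section | Basis for failure | Period |
|---|---|---|
| 4.1, general | subject's report | after Day 7 |
| 4.1, Day 14 paragraph | subject's report | by Day 14 |
| 7.3.4 | subject's report | after Day 14, no end date |
| 5.5.1, item 5 | determination at a revisit | any revisit |
| 7.6 | live lice present | on Day 14 |

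The first two periods can be read together as one interval, Day 7 to Day 14. The third does not fit an endpoint defined as status at Day 14. Item 5 of 5.5.1 also has to be squared with the Day 7 rule in 4.1 and 7.3.3, under which live lice lead to repeat treatment. No section says which rule prevails when a report and an examination disagree.

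**2. Route to the endpoint.** Report after Day 7 → regarded as a failure and offered the alternative product (4.1) → if alternate therapy is needed, discontinued and counted as a failure in mITT and PP (10.2). No step requires a louse to be found.

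**3. The plan's sample size.** Inputs from 10.5: 0.45 versus 0.85, two-sided alpha 0.05, power 0.80.

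- Plain formula: n = [1.960·√(2·0.65·0.35) + 0.842·√(0.45·0.55 + 0.85·0.15)]² / 0.40² = 21.1, so 22 per group.
- With continuity correction: n′ = (n/4)·[1 + √(1 + 4/(0.40n))]² = 25.9, so 26 per group, which is the plan's figure.
- Dropout: 26/0.90 = 28.9, so 29 per group and 58 in all, as stated.

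The need for a continuity correction does not bear on this point. I use 26 per arm below.

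**4. Effect of false reports.** Let a fraction f of truly lice-free subjects in an arm be failed on a mistaken report. The observed lice-free rate is then p(1 − f). The documents give no value for f, so these values are assumptions. I enumerated all outcomes of the pooled two-sided Z test at alpha 0.05. A false win is a significant result favouring the spray when the true rates are equal; the nominal value is 2.5%.

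| True rate, spray / control | f, spray / control | Observed rate | Result |
|---|---|---|---|
| 45% / 45% | 0 / 0 | 45% / 45% | false win 2.4% |
| 45% / 45% | 0 / 10% | 45% / 40.5% | false win 5.1% |
| 60% / 60% | 0 / 0 | 60% / 60% | false win 2.6% |
| 60% / 60% | 0 / 10% | 60% / 54% | false win 6.3% |
| 60% / 60% | 0 / 20% | 60% / 48% | false win 12.9% |
| 60% / 60% | 10% / 0 | 54% / 60% | false win 0.8% |
| 60% / 60% | 10% / 10% | 54% / 54% | false win 2.3% |
| 85% / 45% | 0 / 0 | 85% / 45% | power 89% |
| 85% / 45% | 10% / 0 | 76.5% / 45% | power 67% |
| 85% / 45% | 10% / 10% | 76.5% / 40.5% | power 77% |

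The 45% and 85% rates come from 10.5; 60% is my choice. With equal f of 10% or 20% in both arms, false wins stay between 2.3% and 2.8% at true rates of 45%, 60% and 75%.

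In subjects, f = 10% means 0.10 × 26 × 0.45 = 1.2 control subjects at 45%, or 0.10 × 26 × 0.85 = 2.2 spray subjects at 85%. One reclassified subject moves an arm by 1/26 = 3.8 points.

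Section 10.1 changes method when either group has fewer than 10 lice-free subjects. I did not model that switch.

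**The case against.** Several stronger readings are tempting, and the documents do not support them.

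- **That the plan nowhere rests failure on a finding.** Sections 5.5.1 (item 5) and 7.6 do. The defect is two competing bases for failure, with no rule on which governs.
- **That the reporting period is contradictory throughout.** Only the wording in 7.3.4 is out of line. The Day 14 sentence in 4.1 also directly follows a staff examination, so there a report would normally come with an inspection.
- **That a later report overwrites a clear Day 14 examination.** Section 4.2.2 fixes status at Day 14, the Synopsis and 6.1.7 give the study 14 days plus or minus 3, and nothing in section 10 provides for overwriting. The effect of a later report is undefined.
- **That unverified reports favour the spray.** The direction depends on which arm over-reports, and the documents give no reason to expect one rather than the other.

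Two further objections have weight. The alternative product is offered, and section 10.2 speaks of subjects who need it, so a report alone does not automatically become a failure in the analysis. Staff supply that product and would probably look at the hair first. Also, only reports between the Day 7 visit and the Day 14 examination matter, so 10% in a single arm is a demanding assumption.

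What stands is that no examination is required before failure is assigned, and the text of 4.1 assigns it on the report.

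**Conclusion.** The point holds, as something that should be fixed. An unconfirmed report between Day 7 and Day 14 that leads to the alternative product can settle the primary outcome. The size of the effect rests on two assumptions the documents cannot settle: how often reports are wrong, and whether that differs by arm. A one-sided error of one or two subjects is enough to roughly double the false-win rate at 45%, or to take about 22 points off the planned power (89% − 67%). Equal error in both arms leaves the false-win rate near nominal but still costs power. The after-Day-14 wording is a gap in the endpoint definition, with no demonstrated effect on the result.

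**What to change.** For endpoint classification only, in sections 4.1, 7.3.4 and 10.2:

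1. After the Day 7 visit and up to Day 14, count a failure in the primary analysis only when a trained evaluator has found and recorded at least 1 live louse, at the Day 14 visit or at an unscheduled visit under 7.3.5.
2. State that live lice at Day 7 that lead to the planned repeat treatment are not in themselves a failure.
3. State that reports after the Day 14 examination do not change the Day 14 classification.
4. Say in 10.2 how a subject who receives the alternative product without a recorded louse enters the primary analysis. Report a sensitivity analysis that counts unconfirmed reported failures as failures.
5. Reconcile 4.1 (both places), 5.5.1 item 5, 7.3.4, 7.6 and 10.2 on who determines failure and in what period.

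This takes no position on when, or on what condition, the alternative product is given.

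The cost is protocol wording, one added analysis, and one examination when a subject attends after a report. Evaluators remain unblinded, so confirmation reduces open-label bias without removing it.
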